Inclusion criteria: Cases: 1) **Dysmenorrhea** cases will have: a) average menstrual pain $\geq 5/10$ (0=no pain and 10=the worst imaginable pain) with menses or withdrawal uterine bleeding from cyclic OCs without painkillers, b) menstrual pain in the region between the umbilicus and the perineum, above the level of the inguinal ligament and c) indication the participant has attempted to resolve pain by medical means (including NSAIDs and/or OCs). Participants who endorse bladder symptoms on the phone screen will be preferentially recruited; those who do not endorse bladder symptoms may be determined ineligible. We found our previous questions to have limited predictive value. Notably because we only want to collect the minimum amount of information necessary to determine eligibility on the phone screen, we may not ask all bladder questions (depending on what future statistics show in regards to what bladder questions accurately predict COS). Participants will complete a daily diary to verify menstrual pain during the screening period.³³ To be eligible as a dysmenorrhea case, a participant must indicate menstrual pain $\geq 5/10$ on at least one day during menses in their daily diary. In the circumstance that a participant originally assigned to the dysmenorrhea group does not reach a pain of 5 on any days on the daily diary, this will be handled on a case-by-case basis particularly if they used a continuous around-the-clock, effective pain treatment regimen. They must have no concurrent chronic pain diagnoses that affect daily life or a history of more than 24 migraines per year. 2) **D+COS participants** will meet criteria for Dysmenorrhea cases, with >15 bladder pain on a 0-100 visual analogue scale (VAS) during either first sensation or first urge at assessment visit #1. Initially participants will be enrolled as dysmenorrhea participants and their final eligibility for D+COS will be determined after their assessment #1 visit. 3) Diagnosis of **PBS participants** will be confirmed by medical records indicating chronic (>3 months) pelvic pain (average intensity $\geq 3/10$), pressure, or discomfort related to the bladder accompanied by at least one other urinary symptom such as persistent urge to void or frequency.³⁴ PBS

participants will also have records review to confirm the exclusion of other conditions by clinical examination or cystoscopy if necessary. PBS participants can have other chronic pain conditions.

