Controls: 1) **Healthy control cases** will have a) average pain \leq 3/10 with menses or with withdrawal uterine bleeding from cyclical OCs and b) no concurrent chronic pain diagnoses or \geq 5 migraines in the past year. Healthy controls with < 2 migraines per year will be recruiting preferentially.

Exclusion criteria for dysmenorrhea (and D+COS), PBS and healthy control cases includes: a) presence of active pelvic or abdominal malignancies (primary or metastatic), b) absence of regular menses (including current pregnancy, recent pregnancy, or active breast feeding) c) active genitourinary infection in the last four weeks, d) unable to read or comprehend the informed consent in English, e) unwilling to complete study procedures f) presence of hypertension or risk for developing hypertension, and g) unwilling to withdraw from OCs for at least one cycle prior to the Phase #1 study visit. Participants with a history of epilepsy will not complete the visual unpleasantness task.

Inclusion/Exclusion Criteria for “Special” Healthy Controls and Chronic Pain Participants (Arm 2)

Special Healthy Controls (n=10) will be enrolled under the same inclusion and exclusion criteria as healthy controls, however, special healthy controls will not be required to have regular periods or abstain from hormonal contraception, and will not be assessed for migraines with aura.

Chronic pain cases (n=50) will have a diagnosed, documented (reviewed by PI) chronic pain disorder greater than six months' duration, which has required at least 2 different prescription treatments and/or surgical management. They must report an average pain of at least 5/10 in the last month. We will accept participants with any type of chronic pain (except for individuals with bilateral knee and hand pain) but anticipate many of our chronic pain participants to suffer from fibromyalgia, lower back pain, and chronic pelvic pain (including irritable bowel syndrome).

Of note, special healthy controls or chronic pain cases will not be excluded for unwillingness to undergo internal PPT testing, visual sensory testing, hip or head PPT. These groups may waive these procedures but still remain eligible to choose to participate in rest of the study.

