Exclusion criteria for Chronic pain cases (n=50) and Special Healthy Controls includes a) presence of active pelvic or abdominal malignancies (primary or metastatic), b) pregnancy, c) active genitourinary infection in the last four weeks, d) unable to read or comprehend the informed consent in English, e) unwilling to undergo study procedures (except internal PPT testing, visual sensory testing, hip or head PPT which may be waived in these groups), f) bilateral hand or knee pain, or g) absence of ovaries.

To summarize, Chronic Pain Cases and Special Healthy Controls may have absence of regular menses, hypertension, a history of epilepsy (in which case sensory testing will not be performed) or migraines with aura, and be unwilling/unable to abstain from hormonal contraception.

Phone Screen

All callers will complete a phone screen to assess eligibility before being scheduled for a screen

visit. Because of the drastically different inclusion/exclusion criteria, separate phone screens will be used for arm 1 (healthy control, dysmenorrhea, and PBS participants) than for arm 2 (special healthy control and chronic pain participants). At the end of the phone screen, all callers who complete an arm #1 or arm #2 phone screen will be asked if we have their permission to keep their phone screen information and contact them for future studies. Participants who indicate yes will be added to our recruitment registry study upon study closeout. Eligible callers will be scheduled for a screening visit.

Note we may attempt to match groups for age and demographics. Thus, in some cases, eligibility on the phone screen may vary based on the study's current need for individuals with certain demographics for each group. We may also require dysmenorrhea participants to endorse bladder symptoms on the phone screen in order for them to be eligible to come in for a screen visit.

Procedures Completed During Each Study Visit: During each testing session, participants will have their blood pressure and pulse taken, urine collected, and a urine pregnancy test (unless no uterus) completed.

C1.b Screening Visit: Informed consent will be obtained by a trained research assistant before any questionnaires or study procedures are completed.

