Factor [2], pelvic hyperalgesia: To confirm pelvic hyperalgesia (*but not necessarily pelvic PPT*) is higher in those with bladder pain, we will show bladder pain and pelvic hyperalgesia (both VAS and TIME) are higher in D+COS than healthy pain-free controls (H), dysmenorrhea only (D), and chronic pain patients (P). Similarly bladder pain, pelvic hyperalgesia and pelvic floor pain sensitivity (PPT) are anticipated to be greater in PBS than H, and D.

Factor [3], centrally mediated hyperalgesia: Greater central dysfunction manifest by impaired CPM and reduced bodily pain thresholds in vulnerable subjects will be shown by comparing D+COS, PBS, and P to D and H. We estimate 15 subjects per group will provide adequate power (g-power, a priori t-test, $\alpha=0.05$, $\beta=0.2$). To verify we have adequate phenotyping of CPM, we have included the positive control group with chronic pain (P). We assumed the

[figure not shown]
difference in CPM between healthy subjects and chronic pain patients in this protocol would have an effect size of 0.78 based on a meta-analysis (Lewis et al. 2012). Using a 2.6 allocation ratio, a priori power analysis ($\alpha=0.05$, $\beta=0.2$), suggests we need 20 healthy participants and as many as 50 chronic pain patients to detect a difference in the mean CPM. Additionally, the utilization of 50 chronic pain patients will allow us to use regression to identify up to 5 predicted factors associated CPM with correlation coefficients exceeding 0.3 even after correcting for multiple comparisons ($\alpha=0.05$, $\beta=0.2$) as suggested by an a priori random model power analysis. This will be readily captured as our global study design encompasses a larger sample size (Table X) to handle anticipated secondary analysis and projected needs for completion of Phase #2.

Additional confirmatory analysis: Special healthy control subjects (n=10), we will verify special healthy control subjects do not differ from original enrolled healthy control subjects (n=20) to ascertain chronic subjects (P) participating in the trial are not treated differently under blinded conditions.

For the secondary analysis of Phase #1, we will evaluate the D+COS (provoked bladder pain) phenotype while accounting for menstrual history (including historical OC exposure), hormonal factors, anxiety, and depression. To determine the relative contribution of these secondary variables on bladder pain, we will perform principal component analysis (PCA).

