C1.i Expected outcomes: (1) *Abnormal CPM is the primary predictor of widespread pain sensitivity observed in dysmenorrhea, D+COS and PBS.* Results would be insightful if CPM was worse in participants with D+COS and PBS than those with dysmenorrhea alone because this would indicate CPM mechanisms are involved in COS. On the other hand, if CPM impairments are universal across chronic pain patients, PBS, D, and D+COS compared to healthy controls, this would indicate that pain independent of location and chronicity depends on impaired descending inhibition. This finding would be the basis for developing a physiological biomarker for those at risk of developing CPP/PBS similar to approaches by others identifying risk for chronic pain^{45,79}. On the other hand, some pain conditions such as rheumatoid arthritis¹¹⁴ and trapezius myalgia¹¹⁵ do not seem to exhibit CPM. The vulnerability to conditions unrelated to CPM may involve either inflammatory or specific peripheral nerve events. If CPM does not correlate with widespread pain sensitivity or bladder pain phenotypes in this proposal, we have adequately powered our sample size to detect alternative mechanisms that could be responsible (e.g. menstrual, hormonal, psychological). Nevertheless, consistent with meta-analyses on the menstrual cycle⁵⁴, psychological⁵⁵, and central factors on pain⁵⁶, we anticipate central pain factors to explain the majority of the variance in bladder pain sensitivity. Determining the relative importance of systemic E2 concentrations vs. other modifiable factors such as

menstrual pain will provide insight on the most important mechanisms for reducing bladder pain sensitivity in vulnerable women.

(2) *Pelvic hyperalgesia and severity of menstrual pain are more common in D+COS phenotype vs. dysmenorrhea only.* The identification of clinical biomarkers such as severity of pain after a speculum exam (analogous to the post pelvic floor PPT pain report) can be obtained from our results. Our study results would provide evidence of the significance of this routine clinical exam in reliably predicting bladder sensitivity.

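### Healthy controls are screened more tightly than the case groups for migraine and other chronic pain, so part of any CPM or threshold difference from healthy, and of PBS versus D, may reflect comorbid pain

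*Combined protocol and SAP*

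**What the plan says.** The Arm 1 inclusion criteria (section C1.a) set different limits for each group. For D they state: "They must have no concurrent chronic pain diagnoses that affect daily life or a history of more than 24 migraines per year". D+COS women must first qualify as dysmenorrhea cases, so the same limits apply. For PBS the text says "PBS participants can have other chronic pain conditions", and no migraine limit is given. Healthy controls must have "no concurrent chronic pain diagnoses or \geq 5 migraines in the past year", that is, neither of these, and the next sentence adds "Healthy controls with < 2 migraines per year will be recruiting preferentially".

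Section C1.h makes CPM and bodily pain thresholds a primary outcome. Under Factor [3], greater central dysfunction "will be shown by comparing D+COS, PBS, and P to D and H", where P is the chronic pain group. The test named for the primary outcomes is the pairwise t-test with Bonferroni correction for six comparisons, and no covariates are listed. The secondary analysis is a principal component analysis of bladder pain that accounts for menstrual history, hormones, anxiety and depression. On balancing the groups, the Phone Screen section says only "we may attempt to match groups for age and demographics".

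**The concern.** A comparison with healthy controls is most informative when the groups differ mainly in the condition under study. Here they also differ, by rule, in migraine and other chronic pain. The plan itself expects chronic pain to go with altered CPM: it sizes the P versus H comparison on an effect of 0.78. It then admits other chronic pain to PBS and bars it from H. A deficit in PBS relative to H could therefore come partly from that other pain.

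PBS versus D has a milder form of the same problem, because D excludes chronic pain that affects daily life and PBS does not. It matters because section C1.i would read worse CPM in D+COS and PBS than in D as a sign that CPM mechanisms are involved in cross-organ sensitization. The PBS half of that reading is exposed.

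**Working it through.** **1. The limits side by side (Arm 1 criteria)**

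| Group | Other chronic pain | Migraine |
|---|---|---|
| H | no diagnosis | at most 4 in the past year; fewer than 2 preferred |
| D and D+COS | allowed if it does not affect daily life | up to 24 a year |
| PBS | allowed | no limit stated |

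The permitted migraine ceiling in D and D+COS is 24/4 = 6 times that in H.

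**2. Which contrasts are touched**

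- D+COS versus D: identical limits, so the rules create no difference.
- D or D+COS versus H: migraine and milder chronic pain may differ.
- PBS versus H: migraine and any chronic pain may differ.
- PBS versus D: chronic pain that affects daily life, and more than 24 migraines a year, may occur in PBS only.
- P versus H: the difference in chronic pain is intended, since P is the positive control.

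**3. The plan's own figure**

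Section C1.h uses effect size 0.78, allocation ratio 2.6, alpha 0.05 and power 0.80, and arrives at 20 healthy and as many as 50 chronic pain women. A two-sided two-sample t-test (noncentral t) gives 19 and 50, with power 0.814; at 20 and 50 the power is 0.828. The figure reproduces, so 0.78 can serve as the plan's own value for the effect of chronic pain on CPM.

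**4. Illustration for PBS versus H**

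Assume no true effect of PBS on CPM, and let a share p of PBS women in excess of H have other pain with effect 0.78. The spurious difference is b = p × 0.78. The t-test's noncentrality is b × √(n1·n2/(n1+n2)). With 40 PBS and 20 H (Table X) the multiplier is √(800/60) = 3.65, so p = 50% gives 0.39 × 3.65 = 1.42 on 58 degrees of freedom.

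| Excess share p (assumed) | b (SD) | Significant at 0.05 | Significant at 0.05/6 |
|---|---|---|---|
| 10% | 0.08 | 6% | 1% |
| 30% | 0.23 | 13% | 4% |
| 50% | 0.39 | 29% | 11% |
| 100% | 0.78 | 80% | 55% |

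Section B.1 expects 40 healthy women to complete Phase 1. With 40 versus 40 and p = 50%, the chances are 41% and 18%: a larger control group makes a biased difference easier to detect. The calculation ignores the extra variance from mixing (0.5 × 0.5 × 0.78² = 0.15 on a variance of 1), which would lower the 50% figures slightly.

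PBS versus D has the same Table X sizes (40 and 20), so a given b has the same chance of significance. The excess share should be smaller there, because D may include milder chronic pain.

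**5. D and D+COS versus H**

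The documents give no migraine prevalence and no effect of migraine on CPM. If 20% to 40% of these women had 5 to 24 migraines a year, against 0% of H by rule, and migraine shifted CPM by 0.3 to 0.8 SD, the bias would be 0.2 × 0.3 = 0.06 to 0.4 × 0.8 = 0.32 SD. All four inputs are assumptions.

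**The case against.** The strongest points on the other side are these.

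- The internal comparison is clean. D is a comparator in Factor [3], and D+COS and D share the same limits. This stands in full: the cross-organ sensitization inference from D+COS versus D is not confounded by eligibility.
- The plan does not attribute every deficit to menstrual or bladder pain. If impairment is found in P, PBS, D and D+COS alike, section C1.i says "this would indicate that pain independent of location and chronicity depends on impaired descending inhibition". Other pain in the case groups threatens that reading much less. A reader might infer that the plan's conclusions about dysmenorrhea and bladder pain fall altogether, or that no difference from healthy can be attributed to them. The text does not support that.
- The bias may be small beside the hypothesized effects. Table X puts CPM at 1 to 2 Z for D and D+COS, so 0.06 to 0.32 SD is at most about a third and could not produce such a difference alone. This stands for D and D+COS. It reassures less for PBS: Table X puts PBS at 4 Z but P at 2 to 4 Z, so on that scale a 50% excess would give 0.5 × 2 = 1 to 0.5 × 4 = 2 Z.
- Migraine or other pain may follow from dysmenorrhea. Section B.1 mentions headache and fibromyalgia as co-morbid conditions for which prevention studies might follow, which fits a downstream role. Adjusting for them could then remove part of the effect under study, and H gives almost no overlap from which to estimate an adjustment. This stands, and it rules out making an adjusted model the main answer.
- Safeguards exist. P shows whether the CPM test detects chronic pain, but it does not separate other pain from bladder pain within PBS. The Arm 2 text implies that Arm 1 women are assessed for migraine with aura, but the Arm 1 exclusion list does not include it, and migraine without aura would remain.

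A reader might also infer, from the migraine studies cited in section C1.h, that the plan links migraine to CPM. That citation supports the effect size for bladder pain at first urge, not for CPM or bodily thresholds.

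**Conclusion.** The concern holds for the CPM and bodily threshold contrasts of D, D+COS and PBS with H, and for PBS versus D. The rules fix the direction of the imbalance, and the planned tests, the optional matching and the secondary covariates do not address it. PBS is the most exposed group. D+COS versus D is unaffected.

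The size cannot be determined from the documents. The 0.39 SD figure for PBS versus H rests on an assumed 50% excess of comorbid pain and on carrying the plan's 0.78 over to that pain. The smaller range for D and D+COS is assumed throughout. The supported conclusion is that part of a difference may reflect comorbid pain, which limits how specifically it can be described. It does not make the contrasts uninterpretable.

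**What to change.** Keep the primary t-tests and the eligibility rules. Add to the Phase 1 analysis:

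1. A table of migraine frequency and other chronic pain diagnoses by group.
2. A prespecified sensitivity analysis of CPM and bodily thresholds that repeats D, D+COS and PBS versus H in cases who meet H's migraine and chronic pain limits, and PBS versus D in PBS women who meet D's limits. Read it by estimate and confidence interval, not by significance.
3. A rule for wording: if the restricted estimate shrinks materially, with the meaning of materially set before the data are examined, do not describe the deficit as specific to dysmenorrhea or bladder pain. Shrinkage alone does not prove bias, since the restriction may select the least affected cases.
4. Any covariate-adjusted model as supportive only.

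The screening history, MIDAS and CMSI described in section C1.b are already collected, so the cost is analysis-plan wording and one extra analysis. The downside is precision. With unit SD, the 95% half-width for 40 versus 20 is 2.00 × √(1/40 + 1/20) = 0.55 SD; if half the PBS women remained, 20 versus 20 gives 2.02 × √(1/20 + 1/20) = 0.64 SD.

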Since endometriosis and fibroids are identifiable anatomical conditions but understanding of their mechanistic contribution to dysmenorrhea and bladder pain is limited, we will include confirmed endometriosis participants and fibroids participants mixed within our dysmenorrhea

cohort to determine which effects produced by the primary analysis are due to anatomical conditions.

Participants are divided into two arms. Arm #1 participants include women ages 18-45 with dysmenorrhea, women with painful bladder syndrome (PBS), and healthy controls. Arm #2 includes women ages 18-45 with chronic pain or special healthy controls.

Our hypotheses on mechanisms responsible for the transition of menstrual pain to bladder pain will be tested through the following phases:

Phase #1 (includes Arm #1 and Arm #2 participants): *To determine if dysmenorrhea with concomitant bladder pain sensitivity exhibits neurophysiological features consistent with established CPP.* Women with dysmenorrhea without COS and women with chronic pain conditions outside of the pelvic region will be used as controls. Quantitative sensory testing (QST) and a noninvasive bladder pain test we previously have validated will be used to determine whether impairments in descending inhibition and pelvic sensitivity are responsible for vulnerability to COS in women with dysmenorrhea (with and without COS) and/or CPP.

Phase #2 (includes a subset of Arm #1 participants only): *To differentiate the individual contributions of circulating sex hormones and repeated sensitizing events (painful menses) on descending and peripheral mechanisms of bladder pain.* The same QST/bladder pain measures studied in Phase #1 will be retested within the D+COS and PBS subjects following a one-year randomized trial of cyclical vs. continuous OCs vs. no treatment. We added a second option for those who are randomized to Phase 2 that did not want to commit to their randomized group. They will be asked to come in for an additional assessment visit a year later. Participating in the randomized group is preferable but this will allow us to still obtain the follow up data that is important with these participants even if they choose not to participate in their assigned group.

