Determining the neurophysiological relationship between repeated uterine inflammation, dysmenorrhea, and COS, and how OCs might reverse that influence, could define a new pathway for understanding the etiology of CPP/PBS. Secondly, identifying early markers of risk could ultimately underlie an effective prevention strategy because the onset of PBS is often gradual with limited symptoms.³²

B. Research Design and Methods

B.1. Overview:

Diagram 2: After screening and washout, dysmenorrhea sufferers with and without COS, PBS patients, and chronic pain participants (with and without pelvic pain conditions) will be compared with controls on experimental pain sensitivity tests (**PPT**), which measure descending inhibition (**CPM**) and pelvic and bladder sensitivity (**Phase #1**). Women with dysmenorrhea with COS and PBS will be asked to participate in Phase #2. In Phase #2, a trial of cyclic and continuous OCs

will be used to differentiate the individual contributions of circulating sex hormones and repeated sensitizing events (painful menstrual periods) on descending and peripheral mechanisms of bladder pain. All participants will also complete a yearly follow-up questionnaire for 5 years (for participants who complete phase 2, the year 1 questionnaire will be incorporated into the 12-month testing Assessment #3 testing session).

This study will enroll a total of approximately 1,080 participants (See **Appendix 1**). Of those subjects, all will be enrolled at NorthShore University HealthSystem (NorthShore). This leaves a total of approximately 1,080 participants to be enrolled in arm #1 (1,020) and arm #2 (60) of the study. We anticipate that some arm 1 and arm 2 participants (up to 415 arm 1 and 10 arm 2 participants) may become ineligible after the screen visit and/or daily diary data because their pain levels do not clearly place them into a defined group, they are enrolled as a dysmenorrhea participant but do not show evidence of COS, medical reasons are identified at the screen visit that were not identified during the phone screen, or they become lost to follow-up between the screen and assessment visit. We expect approximately 645 arm 1 and arm 2 participants will continue the study and complete Phase 1; 515 will be women with dysmenorrhea, 40 will be women with PBS, 40 will be healthy women without pelvic pain or painful periods, 7 will be “special” healthy controls, and 43 will be women with chronic pain.

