collected electronically using REDCap at home. If requested, paper versions can be provided instead and mailed in. For participants continuing to Phase 2, the year 1 annual medical history questionnaire will usually take place during their assessment #3 visit. All participants that complete phase 1 (Screen + Assessment #1), including phase 2 dropouts, will be asked to complete the annual follow-up questionnaire.

Group (Sample Size)	H (20)	D (20)	D+COS (95)	PBS (40)	P (50)	MSA
Bladder Pain at FU (VAS)	0	0	2.5	3.0	-	0.85
Pelvic Hyperalgesia (VAS)	0	0	3	3	-	0.84
Pelvic Hyperalgesia (Time)	0	0	2	2.5	-	0.83
Pelvic Pain Thresholds	0	.5	.5	2.3	-	0.81
Bodily Pain Thresholds	0	1.5	2	2	2.3	0.91
Conditioned Pain Modulation	0	1-2	1-2	4 _a	2-4 _b	0.94
Menstrual Pain History	0	3.7	5	6	-	0.81
Temporal Summation	0	0	.7	.8	-	-
Estradiol	0	1-3 _c	1-3 _c	1-3	-	0.84
Depression/Anxiety	0	.3	.4	2	2-4	0.82

Table X: Sample sizes and hypothesized results in Z-scores or range of Z-scores (relative to healthy) for subjects that are healthy (H), have dysmenorrhea (D), have cross organ sensitization (D+COS), PBS, or chronic pain (P). MSA indicates Kaiser's measure of sampling adequacy. Numbers in italics indicated minimum detectable hypothesized score with current sample size. Z-scores based on preliminary data, or others indicated by subscript (a: ⁹, b: ^{11,13}). Effects temporal summation in these populations are unknown, but effect sizes as large as 1.1 have been reported for fibromyalgia. Dashes (-) indicate unknown effect size.

C1.h Data Analysis/Sample Size Requirements: The primary outcomes under this hypothesis will be [1] bladder pain at FU, [2] pelvic hyperalgesia (VAS, time to return to baseline pain), reflecting peripheral dysfunction/sensitization, and [3] centrally mediated hyperalgesia (CPM, bodily pain thresholds).

Factor [1], Bladder pain at FU: Our preliminary data on healthy subjects and women with dysmenorrhea, in combination with other studies investigating migraine and PBS, suggests effect sizes between 1.4-5.6 (Cohen's d). As a control comparison, we expect that women with chronic pain will have levels of bladder and pelvic sensitivity comparable to healthy subjects. We will perform t-tests for each of these three pain variables using pairwise contrasts and appropriate Bonferroni corrections for six group comparisons.

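### The chronic pain group is the non-pelvic control for bladder and pelvic sensitivity, yet entry admits pelvic pain and no analysis rule separates the two

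*Combined protocol and SAP*

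**What the plan says.** - **Section A, Phase #1 aim.** "Women with dysmenorrhea without COS and women with chronic pain conditions outside of the pelvic region will be used as controls".
- **Section C1.h, Factor [1].** "As a control comparison, we expect that women with chronic pain will have levels of bladder and pelvic sensitivity comparable to healthy subjects".
- **Section C1.h, Factor [2].** Bladder pain and pelvic hyperalgesia (pain score and time) are to be shown "higher in D+COS than healthy pain-free controls (H), dysmenorrhea only (D), and chronic pain patients (P").
- **Section B.1, legend to Diagram 2.** "chronic pain participants (with and without pelvic pain conditions) will be compared with controls on experimental pain sensitivity tests".
- **Section C1.a, Arm 2 criteria.** "We will accept participants with any type of chronic pain (except for individuals with bilateral knee and hand pain"), and the investigators "anticipate many of our chronic pain participants to suffer from fibromyalgia, lower back pain, and chronic pelvic pain (including irritable bowel syndrome"). The Arm 2 exclusions remove no pelvic pain, bladder pain or dysmenorrhea.
- **Section C1.h, Factor [3].** P is also the positive control for CPM. The stated size of 20 healthy and up to 50 chronic pain women is derived for that comparison.
- **Table X.** P's bladder and pelvic entries are dashes, which the legend defines as unknown effect size.

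**The concern.** The D+COS v P contrast is there to show that bladder and pelvic hyperalgesia belongs to D+COS and is not a general feature of chronic pain. That needs a chronic pain group without pelvic disease, which is how the Phase 1 aim describes it. The entry criteria and the overview describe a mixed group, and C1.h then uses P whole.

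The protocol gives its own reason to expect this to matter. Section A says that prolonged pelvic pain after a vaginal stimulus is common in chronic pelvic pain patients, and that is the Factor [2] outcome. The aim itself asks whether D+COS resembles established chronic pelvic pain. Women with that condition therefore sit inside a group that D+COS is supposed to exceed.

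What is at stake is interpretation. If P comes out above healthy women, or D+COS v P comes out small or null, there are two explanations: chronic pain raises these measures in general, or the control group contained women with pelvic pain. The plan as written cannot tell them apart.

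**Working it through.** **The plan's own figure.** The only sample size given for P concerns CPM: effect size 0.78, allocation ratio 2.6, α = 0.05, power 0.80. A two-sided two-sample t-test gives power 0.812 at 19 healthy and 49 P, and 0.828 at 20 and 50. The stated 20/50 is reproduced, and this point does not disturb it. No figure is given for D+COS v P on bladder or pelvic outcomes.

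**Inputs from the documents**
- Z-scores, D+COS and PBS (Table X): bladder pain at first urge 2.5 and 3.0; pelvic hyperalgesia score 3 and 3; hyperalgesia time 2 and 2.5. Healthy is 0.
- Group sizes: 95 D+COS, 20 healthy and 50 P (Table X); 43 P expected to complete Phase 1 (B.1).
- Bonferroni correction for six comparisons (C1.h): 0.05/6 = 0.0083.

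**Assumptions, not in the documents**
- A share q of P has a pelvic condition; q is varied.
- Those women score at the PBS value and the rest of P at 0. The PBS value is probably an upper range for women with irritable bowel syndrome.
- The SD is 1 within each component and within D+COS and healthy.

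**Formulas.** With PBS value z:
- mean of P = qz
- SD of P = √(1 + z²q(1−q))
- gap = Z(D+COS) − qz
- SE = √(1/95 + SD²/n_P)

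Power is from the noncentral t with Welch degrees of freedom, two-sided 0.0083.

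**Worked case: bladder pain, q = 0.5, n_P = 43.** Mean 1.5; SD = √(1 + 9 × 0.25) = 1.80; gap = 2.5 − 1.5 = 1.0; SE = √(0.0105 + 3.25/43) = 0.293; noncentrality 1.0/0.293 = 3.41; about 54 df; critical value 2.74; power 0.745. With n_P = 50 the SE is 0.275 and power 0.817.

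| Outcome | q | Mean of P | SD of P | Gap | Power, n_P = 43 to 50 |
|---|---|---|---|---|---|
| Bladder pain | 0.20 | 0.60 | 1.56 | 1.90 | >0.999 |
| | 0.33 | 0.99 | 1.73 | 1.51 | 0.994 to 0.998 |
| | 0.50 | 1.50 | 1.80 | 1.00 | 0.745 to 0.817 |
| Hyperalgesia score | 0.20 | 0.60 | 1.56 | 2.40 | >0.999 |
| | 0.33 | 0.99 | 1.73 | 2.01 | >0.999 |
| | 0.50 | 1.50 | 1.80 | 1.50 | 0.989 to 0.996 |
| Hyperalgesia time | 0.20 | 0.50 | 1.41 | 1.50 | >0.999 |
| | 0.33 | 0.83 | 1.54 | 1.18 | 0.964 to 0.983 |
| | 0.50 | 1.25 | 1.60 | 0.75 | 0.543 to 0.619 |

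**P against healthy (43 v 20, two-sided 0.05, z = 3).** SE = √(SD²/43 + 1/20). At q = 0.20 this is √(2.44/43 + 0.05) = 0.327 and the noncentrality is 0.60/0.327 = 1.84. The chance of a significant difference is 0.44 at q = 0.20, 0.80 at 0.33 and 0.99 at 0.50. Section B.1 expects 40 healthy completers; with 40 rather than 20 these chances would be higher.

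**Size after restriction.** If 25 of 50 P women remain, and taking a 1 SD gap purely for illustration, the noncentrality is 1/√(1/95 + 1/25) = 4.45 on 118 df against a critical value of about 2.68, and power is about 0.96. With only 9 of 43 left, power for a gap of 2.0, the smallest D+COS value among these outcomes, is 0.999.

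**The case against.** The strongest defence is that the documents already contain both halves of a sensible design. Section A names the non-pelvic women as the control and also speaks of studying women with chronic pelvic pain; B.1 openly lists both kinds. On that reading, pelvic P is a studied group, non-pelvic P is the control, and one linking sentence is missing from C1.h. The gap is indeed that narrow, but it is real: C1.h names the comparator simply as chronic pain patients (P). Broad entry is also reasonable for CPM, the comparison that sets the size of P.

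Two stronger readings are tempting, and the documents support neither.

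- A reader might infer that a mixed control invalidates a positive D+COS v P result. It does not. Pelvic-pain women raise P and shrink the gap, so a significant excess of D+COS over P is conservative in this respect.
- A reader might infer that the contrast loses its power at modest pelvic shares. That needs a much smaller true gap than the plan assumes. With a 1 SD gap shrunk to 0.67 or 0.50 SD, 95 v 50 gives about 87% and 57% power at equal SDs. Nothing in the documents states a 1 SD gap; Table X gives 2 to 3.

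It is also fair that no formal equivalence test of P against healthy is planned, so matching healthy women is an expectation and not a tested claim.

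**Conclusion.** The inconsistency stands. The aim and C1.h require a non-pelvic chronic pain control, eligibility and the overview describe a mixed group, and no analysis rule bridges them. The bias runs toward the null for D+COS v P. The main casualties are the expectation that P resembles healthy women and the reading of a null or reduced contrast.

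Under the upper-range assumption, the first would probably fail at a pelvic share of about one third (chance 0.80 on bladder pain). Power for D+COS v P is at least 0.96 up to that share. At one half it falls to 0.75–0.82 for bladder pain and 0.54–0.62 for hyperalgesia time, and stays near 0.99 for the hyperalgesia score. The true share and these women's scores are unknown, so confidence is high in the mismatch and limited in its size. It should be corrected, but it does not undermine the trial.

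**What to change.** Reconcile section A, the B.1 overview, the Arm 2 criteria and C1.h so that they describe one group with a stated role for each outcome. Then prespecify:

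1. For Factors [1] and [2], the control is P women whose documented diagnosis or history at entry is non-pelvic: no diagnosis of chronic pelvic pain, irritable bowel syndrome, PBS or vulvodynia. The chronic pain diagnosis is already reviewed at entry and a medical and gynecological history is already taken.
2. The split is not made on the Genitourinary Pain Index or other symptom scores close to the outcome. Removing women for bladder symptoms would help to make P look healthy and would inflate the specificity claim.
3. Pelvic-pain P is reported separately, and all of P is given as a sensitivity analysis.
4. All of P remains the positive control for CPM (Factor [3]), which leaves the 20/50 calculation intact.
5. The number of P women contributing internal pelvic data is reported, because that testing may be waived in Arm 2.

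The cost is analysis wording, a classification made from records already held, and a smaller P for Factors [1] and [2]. The power after restriction shown in the working suggests that the smaller group is affordable.
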